5.3.1.1 EORTC QLQ-C30

The EORTC QLQ-C30 is a 30-item self-administered questionnaire (see [Appendix F](#)). There are 9 multiple item scales: 5 scales that assess aspects of functioning (physical, role, cognitive, emotional, and social), 3 symptom scales (fatigue, pain, and nausea and vomiting), and a global health status/QoL scale. There are 5 single-item measures assessing additional symptoms commonly reported by cancer patients (dyspnea, loss of appetite, insomnia, constipation, and diarrhea) and a single item concerning the perceived financial impact of the disease. All but 2 questions have 4-point scales: "Not at all," "A little," "Quite a bit," and "Very much." The 2 questions concerning global health status and QoL have 7-point scales with ratings ranging from "Very poor" to "Excellent." For each of the 15 domains (9 multiple-item scales and 6 single item scales), final scores are

transformed such that they range from 0 to 100, where higher scores indicate greater functioning, greater QoL, or greater level of symptoms ([Aaronson et al 1993](#)).

5.3.1.2 EORTC QLQ-H&N35

The EORTC QLQ-H&N35 module is a 35-item self-administered questionnaire (see [Appendix F](#)). There are 7 multiple item scales that assess pain in the mouth, problems with swallowing, senses, speech, social eating, social contact, and sexuality. There are 11 single-item measures assessing additional symptoms commonly reported by head and neck cancer patients, including problems with teeth, problems with mouth opening, dry mouth, sticky saliva, coughing, feeling ill, use of analgesics, use of nutritional supplements, use of a feeding tube, weight gain, and weight loss. All but 5 questions have 4-point scales: “Not at all,” “A little,” “Quite a bit,” and “Very much.” The 5 questions concerning use of analgesics, use of nutritional supplements, use of a feeding tube, weight gain, and weight loss have 2-point scales (“Yes” or “No”). For each of the 18 domains (7 multiple-item scales and 11 single-item scales), final scores are transformed such that they range from 0 to 100, where higher scores indicate greater level of symptoms ([Singer et al 2013](#)).

5.3.1.3 CCI [REDACTED]

CCI [REDACTED]

5.3.1.4 CCI [REDACTED]

CCI [REDACTED]

5.3.1.5 CCI [REDACTED]

CCI [REDACTED]

CCI

5.3.2 Administration of the patient-reported outcome questionnaires

Patients will complete the PRO assessments by using a handheld ePRO device.

Each center must allocate the responsibility for the administration of the PRO devices to a specific individual (eg, a research nurse or study coordinator) and, if possible, assign a back-up person to cover if that individual is absent. The PRO questionnaires must be completed per the schedule of assessments (see [Table 2](#), [Table 3](#), and [Table 4](#)). Patients will be instructed to bring their handheld devices to every clinic visit. In instances where the PRO assessments coincide with a clinic visit, the research nurse or study coordinator should verify that the questionnaire was completed before the visit. If not, the patient should complete the questionnaire prior to any other study procedures and before discussion of disease progression to avoid biasing the patient's responses to the questions.

The following best practice guidelines should be followed when collecting PRO data via an electronic device:

- The research nurse or appointed site staff must explain the value and relevance of participation to patients and inform them that these questions are being asked in order to find out from them directly how they feel. This can help motivate patients to comply with data collection. The research nurse or appointed site staff should also stress that the information is confidential. Therefore, if the patient has any medical problems, he/she should discuss them with the doctor or research nurse separately from the ePRO assessment.
- The research nurse or appointed site staff must train the patient on how to use the ePRO device using the materials and training provided by the ePRO vendor, and also provide guidance on whom to call if there are problems with the device.
- The research nurse or appointed site staff must remind patients that there are no right or wrong answers and avoid introducing bias by not clarifying items. The patient should not receive help from relatives, friends, or clinic staff to answer the PRO questionnaires.

- The research nurse or appointed site staff must monitor compliance; minimizing missing data is a key aspect of study success. Compliance must be checked at each study visit and should be checked more frequently to identify problems early. If compliance drops below 85%, a check-in call from the site to ask the patient if he/she has any difficulties is highly recommended.

5.3.3 WHO/ECOG performance status

WHO/ECOG performance status will be assessed at the times specified in the assessment schedules (see [Table 2](#), [Table 3](#), and [Table 4](#)) based on the following:

0 = Fully active; able to carry out all usual activities without restrictions

1 = Restricted in strenuous activity but ambulatory and able to carry out light work or work of a sedentary nature, eg, light housework, office work

2 = Ambulatory and capable of self-care but unable to carry out any work activities. Up and about more than 50% of waking hours

3 = Capable of only limited self-care; confined to bed or chair more than 50% of waking hours

4 = Completely disabled; unable to carry out any self-care and totally confined to bed or chair

Any significant changes from baseline or screening must be reported as an AE.

5.4 Pharmacokinetics

5.4.1 Collection of samples and determination of drug concentration

Blood samples for determination of MEDI4736 and tremelimumab concentration in serum will be obtained according to the assessment schedules (see [Table 2](#) and [Table 4](#)).

Samples for determination of MEDI4736 and tremelimumab concentration in serum will be analyzed by a designated third party on behalf of AstraZeneca. Samples will be collected, labeled, stored, and shipped as detailed in the Laboratory Manual. Full details of the analytical method used will be described in a separate Bioanalytical Validation Report.

5.4.2 Collection of samples to measure for the presence of anti-drug antibodies

The presence of ADA will be assessed in serum samples taken according to the assessment schedules (see [Table 2](#) and [Table 4](#)).

Samples will be measured for the presence of ADAs and ADA-neutralizing antibodies for both IPs (MEDI4736 and tremelimumab) using validated assays. Tiered analysis will be performed to include screening, confirmatory, and titer assay components, and positive-negative cut points previously statistically determined from drug-naïve validation samples will be employed.

5.4.3 Storage and destruction of pharmacokinetic/anti-drug antibody samples

PK and ADA samples will be disposed of a maximum of 10 years after the IPs are approved for marketing.

PK and ADA samples may be disposed of or destroyed and anonymized by pooling. Additional analyses may be conducted on the anonymized, pooled PK samples to further evaluate and validate the analytical method. Results from such analyses may be reported separately from the clinical study report (CSR).

Incurred sample reproducibility analysis, if any, will be performed alongside the bioanalysis of the test samples. The results from the evaluation will not be reported in the CSR but separately in a Bioanalytical Validation Report.

CCI [REDACTED]

5.5 Biomarker analysis

The patient's consent to the use of donated biological samples is mandatory. Tissue samples will be obtained from all screened patients.

Pretreatment tumor PD-L1 expression will be evaluated in all randomized patients. Data will be compared between arms to determine if baseline PD-L1 status is prognostic and/or predictive of outcomes associated with MEDI4736 + tremelimumab combination therapy or MEDI4736 monotherapy versus SoC. Baseline tumor requirements are briefly described in Section 5.5.1.

CCI [REDACTED]

Details for collection, volumes, storage, and shipment of biologic samples are presented in a separate Laboratory Manual.

All samples collected for biomarker analyses will be stored at the study site, a reference laboratory, or at AstraZeneca facilities and may be used for subsequent research relevant to evaluating biological and/or clinical response to immunotherapy.

The results may be pooled with biomarker data from other MEDI4736 + tremelimumab combination therapy studies to evaluate biological responses across indications and to compare results in monotherapy versus combination settings.

5.5.1 Collection of patient samples for stratification by PD-L1

At screening, there is a mandatory provision of formalin-fixed and paraffin-embedded tissue to be used for determination of eligibility. For the MEDI4736 + tremelimumab combination therapy arm only, **there is a subsequent mandatory provision of tissue if**

retreatment is planned unless, after discussion with Study Physician, biopsy is not clinically feasible:

- **MANDATORY:** Provision of a newly acquired tumor sample (preferred) **OR** archival tissue obtained within 3 years. **ONLY** 1 sample (either newly acquired or archival tissue) will be used to assess PD-L1 status for purposes of eligibility. Where multiple samples have been submitted for the same patient, results from the most recent evaluable sample will inform patient status for eligibility.

Samples should be collected via a core needle of 18 gauge or larger or be collected as an excisional tumor biopsy sample. Where institutional practice, in this setting, uses a smaller gauge needle, samples should be submitted in sufficient number to ensure that availability of result can be achieved.

When tissue is newly obtained using an 18-gauge needle for the purpose of entry into this study, 2 cores should be placed in formalin and processed to a single paraffin-embedded block, as described in the Laboratory Manual. When a smaller gauge needle is used, the number of cores rises to 3 or 4.

The tumor specimen submitted to establish eligibility should be of sufficient quantity to allow for PD-L1 IHC analyses (see the Laboratory Manual). Samples with limited tumor content and fine needle aspirates are inadequate for defining tumor PD-L1 status.

Tumor lesions used for newly acquired biopsies should not be the same lesions used as RECIST 1.1 target lesions, unless there are no other lesions suitable for biopsy. In this instance, only core needle (not excisional/incisional) biopsy is recommended. For patients with a single target lesion being used for a screening biopsy for PD-L1 testing, allow approximately 2 weeks before acquiring imaging scans for baseline tumor assessment.

- **CCI** [REDACTED]
- **OPTIONAL:** The collection of additional archived tumor tissue block (formalin-fixed paraffin-embedded) is highly encouraged, where such samples exist in a quantity sufficient to allow for analysis. This specimen may be supplied at any time during the study. Tumor tissue block is preferred. If a tissue block is unavailable, unstained sections from the tissue block may be submitted. Please consult the Laboratory Manual for specific instructions and guidelines regarding sections.
- **OPTIONAL:** The collection of additional biopsies (other than the mandatory tissue biopsy required prior to retreatment for patients in the MEDI4736 + tremelimumab combination therapy arm) is strongly encouraged.

Additional tumor biopsies collected as part of clinical care (eg, for mixed responses or upon PD) can be submitted for further analysis.

See the Laboratory Manual for further details of requirements including sample QC and shipping.

CCI [Redacted]

The analytically validated VENTANA PD-L1 SP263 IHC assay will be used to determine PD-L1 IHC status in this study for the purposes of stratification and for the analysis of the original diagnostic sample.

To meet the requirement of FDA approval of a companion diagnostic, sections of the tumor will be retained at VENTANA for potential additional studies, as requested by the FDA, to support potential test approval.

5.5.2 Collection of exploratory biomarker data

5.5.2.1 CCI [Redacted]

CCI [Redacted]

[Redacted]

[Redacted]

[Redacted]

[Redacted]

CCI

5.5.2.2 CCI

CCI

5.5.3 Management of biomarker data

CCI

5.5.4 Storage, re-use, and destruction of biological samples

Samples will be stored for a maximum of 15 years from the end of study, after which they will be destroyed. The results of this biomarker research may be reported in the CSR itself, as an addendum, or separately in a scientific report or publication. The results of this biomarker research may be pooled with biomarker data from other studies involving MEDI4736 to generate hypotheses to be tested in future research.

5.5.5 Labeling and shipment of biological samples

The Principal Investigator will ensure that samples are labeled and shipped in accordance with the Laboratory Manual and the Biological Substance, Category B, Regulations (materials containing or suspected to contain infectious substances that do not meet Category A criteria); see [Appendix C](#) “International Air Transportation Association 6.2 Guidance Document.”

Any samples identified as Infectious Category A materials will not be shipped, and no further samples will be taken from the involved patients unless agreed upon with AstraZeneca and appropriate labeling, shipment, and containment provisions are approved.

5.5.6 Chain of custody of biological samples

A full chain of custody will be maintained for all samples throughout their life cycle.

The Principal Investigator at each center will keep full traceability of collected biological samples from the patients while in storage at the center until shipment or disposal (where appropriate) and will keep documentation of receipt of arrival.

The sample receiver will keep full traceability of the samples while in storage and during use until used or disposed of or until further shipment and will keep documentation of receipt of arrival.

AstraZeneca will keep oversight of the entire life cycle through internal procedures, monitoring of study sites, and auditing of external laboratory providers.

Samples retained for further use will be registered in the AstraZeneca Biobank system during the entire life cycle.

5.5.7 Withdrawal of informed consent for donated biological samples

If a patient withdraws consent to the use of donated biological samples, the samples will be disposed of or destroyed and the action documented. If samples have already been analyzed, AstraZeneca is not obliged to destroy the results of this research.

The Principal Investigator will:

- Ensure that AstraZeneca is immediately notified of the patients’ withdrawal of informed consent to the use of donated samples
- Ensure that biological samples from that patient, if stored at the study site, are immediately identified, disposed of or destroyed and the action documented
- Ensure that the laboratory(ies) holding the samples is/are immediately informed about the withdrawn consent and that samples are disposed of or destroyed, the action is documented, and the signed document is returned to the study site
- Ensure that the patient and AstraZeneca are informed about the sample disposal

5.6 Pharmacogenetics (not applicable)

Not applicable.

5.7 Pharmacodynamics (not applicable)

Not applicable.

6. SAFETY REPORTING AND MEDICAL MANAGEMENT

The Principal Investigator is responsible for ensuring that all staff involved in the study are familiar with the content of this section.

6.1 Definitions of serious adverse events

An SAE is an AE occurring during any study phase (ie, screening, treatment, washout, or follow-up) that fulfills one or more of the following criteria:

- Results in death
- Is immediately life-threatening
- Requires in-patient hospitalization or prolongation of existing hospitalization
- Results in persistent or significant disability or incapacity or substantial disruption of the ability to conduct normal life functions
- Is a congenital abnormality or birth defect
- Is an important medical event that may jeopardize the patient or may require medical intervention to prevent one of the outcomes listed above

For further guidance on the definition of an SAE, see [Appendix B](#).

6.2 Recording of adverse events

6.2.1 Time period for collection of adverse events

AEs and SAEs will be collected from the time of signature of informed consent throughout the treatment period and including the follow-up period (up to 90 days after the last dose of IP or until initiation of another therapy). AEs and SAEs collected prior to randomization will be reported as pre-randomization AEs and SAEs.

6.2.2 Follow-up of unresolved adverse events

During the course of the study, all AEs and SAEs should be proactively followed up for each patient. Every effort should be made to obtain a resolution for all events, even if the events continue after discontinuation or study completion.

Any AEs that are unresolved at the patient's last visit in the study are followed up by the Investigator for as long as medically indicated, but without further recording in the eCRF. AstraZeneca retains the right to request additional information for any patient with ongoing AE(s)/SAE(s) at the end of the study, if judged necessary.

6.2.3 Variables

The following variables will be collected for each AE:

- AE (verbatim)
- The date when the AE started and stopped
- The maximum CTCAE grade reported
- Changes in CTCAE grade
- Whether the AE is serious or not
- Investigator causality rating against the IP (yes or no)
- Action taken with regard to IP
- Administration of treatment for the AE
- Whether the AE caused the patient's withdrawal from the study (yes or no)
- Outcome

In addition, the following variables will be collected for SAEs:

- Date the AE met criteria for SAE
- Date the Investigator became aware of the SAE
- Seriousness criteria fulfilled
- Date of hospitalization
- Date of discharge
- Probable cause of death
- Date of death
- Whether an autopsy was performed
- Causality assessment in relation to study procedure(s)
- Description of the AE

The grading scales found in the revised NCI CTCAE version 4.03 will be utilized for all events with an assigned CTCAE grading. For those events without assigned CTCAE grades, the recommendation in the CTCAE criteria that converts mild, moderate, and severe events into CTCAE grades should be used. A copy of the CTCAE version 4.03 can be downloaded from the Cancer Therapy Evaluation Program website (<http://ctep.cancer.gov>).

It is important to distinguish between serious and severe AEs. Severity is a measure of intensity, whereas seriousness is defined by the criteria in Section 6.1. An AE of severe intensity need not necessarily be considered serious. For example, nausea that persists for several hours may be considered severe nausea, but it is not an SAE unless it meets the criteria shown in Section 6.1. On the other hand, a stroke that results in only a limited degree of disability may be considered a mild stroke, but it would be an SAE if it satisfies the criteria shown in Section 6.1.

6.3 Definition of adverse events

An AE is the development of an undesirable medical condition or the deterioration of a pre-existing medical condition during or following exposure to a pharmaceutical product, whether or not the condition is considered to be causally related to the product. An undesirable medical condition can be a symptom (eg, nausea or chest pain), sign (eg, tachycardia or enlarged liver), or the abnormal result of an investigation (eg, laboratory findings or ECG). In clinical studies, an AE can include an undesirable medical condition occurring at any time, including run-in or washout periods, even if no study treatment has been administered.

The term ‘AE’ is used to include both serious and non-serious AEs.

6.3.1 Causality collection

The Investigator will assess the causal relationship between the IP and each AE and answer “yes” or “no” to the question “Do you consider that there is a reasonable possibility that the event may have been caused by the investigational product?”

For SAEs, causal relationship will also be assessed for other medications and study procedures. Note that, for SAEs that could be associated with any study procedure, the causal relationship is implied as “yes.”

A guide to the interpretation of the causality question is found in [Appendix B](#).

6.3.2 Relationship to protocol procedures

The Investigator is also required to provide an assessment of the relationship of SAEs to protocol procedures on the SAE report form. This includes both non-treatment-emergent (ie, SAEs that occur prior to the administration of IP) and treatment-emergent SAEs. A protocol-related SAE may occur as a result of a procedure or intervention required during the study (eg, blood collection). The following guidelines should be used by Investigators to assess the relationship of SAEs to the protocol:

- Protocol related: The event occurred due to a procedure or intervention that was described in the protocol for which there is no alternative etiology present in the patient’s medical record.
- Not protocol related: The event is related to an etiology other than the procedure or intervention that was described in the protocol. The alternative etiology must be documented in the study patient’s medical record.

6.3.3 Adverse events based on signs and symptoms

All AEs spontaneously reported by the patient or reported in response to the open question from the study personnel: “Have you had any health problems since the previous visit/you were last asked?” or revealed by observation will be collected and recorded in the eCRF. When collecting AEs, the recording of diagnoses is preferred, when possible, to recording a list of signs and symptoms. However, if a diagnosis is known and there are other signs or symptoms that are not generally part of the diagnosis, the diagnosis and each sign or symptom will be recorded separately.

6.3.4 Adverse events based on examinations and tests

The results from protocol-mandated laboratory tests and vital signs measurements will be summarized in the CSR. Deterioration as compared to baseline in protocol-mandated laboratory values and vital signs should therefore only be reported as AEs if they fulfill any of the SAE criteria or are the reason for discontinuation of treatment with the IP.

If deterioration in a laboratory value or vital sign is associated with clinical signs and symptoms, the sign or symptom will be reported as an AE and the associated laboratory result or vital sign will be considered as additional information. Whenever possible, the reporting Investigator should use the clinical rather than the laboratory term (eg, anemia versus low hemoglobin value). In the absence of clinical signs or symptoms, clinically relevant deteriorations in non-mandated parameters should be reported as AEs.

Deterioration of a laboratory value that is unequivocally due to disease progression should not be reported as an AE/SAE.

Any new or aggravated clinically relevant abnormal medical finding at a physical examination as compared with the baseline assessment will be reported as an AE.

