6.7 Management of IP-related toxicities

The following general guidance should be followed for management of toxicities.

- Treat each of the toxicities with maximum supportive care (including holding the agent suspected of causing the toxicity if required).
- If the symptoms promptly resolve with supportive care, consideration should be given to continuing the same dose of the assigned IP along with appropriate continuing supportive care. If medically appropriate, dose modifications are permitted.
- All dose modifications should be documented with clear reasoning and documentation of the approach taken.

All toxicities will be graded according to NCI CTCAE, version 4.03.

As with any antibody, allergic reactions to dose administration are possible. Appropriate drugs and medical equipment to treat acute anaphylactic reactions must be immediately available, and study personnel must be trained to recognize and treat anaphylaxis. The study site must have immediate access to emergency resuscitation teams and equipment in addition to the ability to admit patients to an intensive care unit if necessary.

6.7.1 MEDI4736 + tremelimumab combination therapy and MEDI4736 monotherapy adverse events of special interest

Adverse events of special interest (AESIs) are events of scientific and medical interest specific to the further understanding of the MEDI4736 and tremelimumab safety profile and require close monitoring and rapid communication by the Investigator to AstraZeneca. MEDI4736 and tremelimumab AESIs may be serious or non-serious. The rapid reporting of these AESIs allows ongoing analysis of these events in order to characterize and understand them in association with the use of these IPs.

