AESIs for MEDI4736 +/- tremelimumab include but are not limited to events with a potential inflammatory or immune-mediated mechanism and which may require more frequent monitoring and/or interventions such as steroids, immunosuppressants, and/or hormone replacement therapy. These AESIs are being closely monitored in clinical studies with MEDI4736 monotherapy and combination therapy. An immune-related adverse event (irAE) is defined as an AE that is associated with drug exposure and is consistent with an immune-mediated mechanism of action and where there is no clear alternate etiology. Serologic, immunologic, and histologic (biopsy) data, as appropriate, should be used to support an irAE diagnosis. Appropriate efforts should be made to rule out neoplastic, infectious, metabolic, toxin, or other etiologic causes of the irAE.

If the Investigator has any questions in regard to an AE being an irAE, the Investigator should promptly contact the Study Physician.

AESIs observed with MEDI4736 +/- tremelimumab include the following:

- Diarrhea / Colitis and intestinal perforation
- Pneumonitis / ILD
- Hepatitis/transaminase increases
- Neuropathy/neuromuscular toxicity (eg, Guillain-Barré, and myasthenia gravis)
- Endocrinopathy (ie, events of hypophysitis/hypopituitarism, adrenal insufficiency, and hyper- and hypothyroidism and type I diabetes mellitus)
- Rash / Dermatitis
- Nephritis / Blood creatinine increases
- Pancreatitis / serum lipase or amylase increases
- Myocarditis
- Myositis / Polymyositis
- Other inflammatory responses that are rare / less frequent with a potential immune-mediated aetiology include, but are not limited to, pericarditis, sarcoidosis, uveitis and other events involving the eye, skin, haematological and rheumatological events.

In addition, infusion-related reactions and hypersensitivity/anaphylactic reactions with a different underlying pharmacological aetiology are also considered AESIs.

Further information on these risks (eg, presenting symptoms) can be found in the current versions of the MEDI4736 and tremelimumab IBs. More specific guidelines for their

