### **Immune-mediated Adverse Events (imAE)**

Immune-mediated Adverse Events (imAE) will be identified from both AESIs and AEPIs based on programmatic rules that consider interventions involving systemic steroid therapy, immunosuppressant use, and/or endocrine therapy (which, in the case of AEPIs, occurs after first considering an Investigator's causality assessment and/or an Investigator's designation of an event as immune-mediated). Further details are provided in an imAE Charter v6.

In addition, the Sponsor may perform medical review of those AESIs and classify them as imAEs or not imAEs via an independent manual adjudication process.

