#### **4.2.13.2 Laboratory assessments**

Data obtained up until the 90 days following discontinuation of IP or until the initiation of the first subsequent therapy following discontinuation of IP (whichever occurs first) will be used for reporting. This will more accurately depict laboratory toxicities attributable to IP only as a number of toxicities up to 90 days following discontinuation of IP are likely to be attributable to subsequent therapy.

Data summaries and listings will be provided in International System (SI) of units.

All laboratory data will be listed. Flags will be applied to values falling outside - reference ranges (which will be explicitly noted on these listings where applicable), and to values for which CTCAE grading applies.

Scatter plots (shift plots) of baseline to maximum/minimum value (as appropriate) on treatment (i.e. on treatment is defined as data collected between the start of treatment and the relevant follow-up period following the last dose of IP) may be produced for certain parameters if warranted after data review.

Boxplots of absolute values by week, and boxplots of change from baseline by week, may be presented for certain parameters if warranted after data review up to Week 40.

Shift tables for laboratory values by worst common toxicity criteria (CTCAE) grade will be produced, and for specific parameters separate shift tables indicating hyper- and hypo-directionality of change will be produced. The laboratory parameters for which CTCAE grade shift outputs will be produced are:

- Hematology: Hemoglobin, Leukocytes, Lymphocytes, absolute count, Neutrophils, absolute count, Platelets
- Clinical chemistry: ALT, AST, Alkaline Phosphatase (ALP), Total bilirubin, Albumin, Magnesium – hypo and – hyper, Sodium – hypo and – hyper, Potassium – hypo and – hyper, Corrected calcium – hypo and – hyper, Glucose – hypo and – hyper, GGT, Creatinine

For the parameters with no CTCAE grading that are listed in the CSP, shift tables from baseline to worst value on treatment will be provided. Additional summaries will include a

shift table for urinalysis (Bilirubin, Blood, Glucose, Ketones, Protein) comparing baseline value to maximum on treatment value.

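### Protocol 6.3.4 and 6.7.1 conflict, with no stated precedence, on recording non-serious laboratory AESIs, so the AESI and imAE tables may be incomplete or differ by site

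*Protocol*

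**What the plan says.** Protocol 6.3.4 sets the rule for laboratory findings. For tests that the protocol requires, worsening from baseline in "laboratory values and vital signs should therefore only be reported as AEs if they fulfill any of the SAE criteria or are the reason" that IP was stopped. The justification it gives is that results of mandated tests will be summarised in the study report anyway. When a laboratory change comes with symptoms, the symptom is the AE and the result is supporting information. Clinically relevant changes without symptoms are reportable only for tests that are not mandated. Section 5.2.1 sends the reader to 6.3.4 and adds no exception.

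Protocol 6.7.1 lists the AESIs. Among them are "Hepatitis/transaminase increases", "Pancreatitis / serum lipase or amylase increases" and blood creatinine increases (paired with nephritis). It states that "MEDI4736 and tremelimumab AESIs may be serious or non-serious" and asks investigators to tell the sponsor about them quickly.

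The SAP identifies AESIs from the preferred terms of AEs (3.3.1 and 4.2.13.1). Immune-mediated AEs "will be identified from both AESIs and AEPIs based on programmatic rules that consider interventions involving systemic steroid therapy", immunosuppressants or endocrine treatment. Laboratory data are reported separately in SAP 4.2.13.2. The chemistry list for CTCAE-grade shift tables begins "Clinical chemistry: ALT, AST, Alkaline Phosphatase (ALP), Total bilirubin, Albumin, Magnesium" and also includes creatinine, but not amylase or lipase.

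**The concern.** One section names certain laboratory increases as events of special interest whether or not they are serious. Another tells the site not to enter them as AEs unless they are serious or end treatment. The AESI and imAE tables are the plan's main description of checkpoint-inhibitor toxicity: incidence, causality, immunosuppressant use, outcome and time to resolution. If an increase never becomes an AE record, none of those outputs can include it, and the count for these categories depends partly on which section a site reads. The trial is open-label and its safety objective compares arms, so the counting rule should be the same everywhere.

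**Working it through.** There is no planned figure to reproduce. The check follows one event through the documents: an increase in ALT, AST, creatinine, amylase or lipase that causes no symptoms, is not serious and does not stop IP.

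1. **Is the test mandated?** Yes. All five are in protocol Table 5 and are drawn on the schedules in Tables 2 to 4, so the allowance in 6.3.4 for non-mandated tests does not apply.
2. **Is it an AE under 6.3.4?** No. Neither trigger (an SAE criterion, or being the reason for stopping IP) is met.
3. **Is it an AESI under 6.7.1?** Yes, by name, and non-serious events are included. The general AE definition in 6.3 also covers abnormal laboratory findings.
4. **Which section prevails?** Neither says. Section 6.7.1 does not claim to override 6.3.4, and 6.3.4 makes no exception for AESIs.
5. **What reaches the AESI tables?** Only events with an AE preferred term. Under 6.3.4 this event has none; under 6.7.1 it does.
6. **What reaches the imAE tables?** Only AESIs and AEs of possible interest that pass rules based on steroid, immunosuppressant or endocrine treatment. The loss here is narrower: increases that received such treatment without IP being stopped and without being judged serious.
7. **Do the laboratory outputs replace the lost record?** In part. All values are listed and flagged, ALT, AST and creatinine have grade shifts, and ALT, AST and bilirubin have threshold summaries. But causality, action taken with IP, treatment given and outcome are collected per AE (protocol 6.2.3), and no laboratory table supplies them. Amylase and lipase are not in the named grade-shift list. SAP 4.2.13.2 promises baseline-to-worst shifts for tests without CTCAE grading, but does not say whether these two fall there.

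**Size.** Within an arm, the uncounted proportion is p × (1 − s) × f. Here p is the proportion of patients with a laboratory-only AESI increase, s is the share of those reportable anyway (serious, or the reason for stopping IP), and f is the share at sites that apply 6.3.4. The documents give none of the three, overall or by arm, so the formula shows what the loss depends on but yields no number.

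**The case against.** The case for leaving the text alone has substance. Section 6.7.1 is the more specific provision, and the general AE definition includes laboratory findings, so a site could reasonably report these increases. Section 6.3.3 prefers a diagnosis to a list of signs, and 6.3.4 prefers the clinical to the laboratory term, so a treated case may well be entered as hepatitis or pancreatitis. A case needing intervention may count as an important medical event under 6.1, which makes it serious and so reportable under 6.3.4. A non-serious increase that stops IP is also reportable. The values themselves are not lost.

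All of this stands and narrows the point. It does not settle which section governs the remaining events: laboratory-only, non-serious, and not the reason for stopping IP.

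Three stronger readings go too far:

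- **That the tables are certain to under-count.** This holds only where sites follow 6.3.4. Where practice is mixed, the problem is inconsistency between sites.
- **That the sponsor loses its rapid notice.** Section 6.3.4 governs what is entered as an AE and does not cancel the communication duty in 6.7.1. Combined transaminase and bilirubin rises also have their own notification route in Appendix D.
- **That the bias falls mainly on the immunotherapy arms.** Section 6.3.4 applies to every arm, chemistry is scheduled on standard of care too, and no rates by arm are given.

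**Conclusion.** The two protocol sections are in unresolved conflict, and the SAP's AESI and imAE tables inherit it. Where 6.3.4 is followed, non-serious laboratory-only AESIs that do not stop IP are missing from the AESI tables, and a smaller set is missing from the imAE tables. Where 6.7.1 is followed, they are present. Ascertainment is therefore incomplete or uneven across sites. This conclusion rests on the text alone; it assumes only that some sites apply 6.3.4 as written. A reader might go on to estimate how many patients are missed per arm, but any such figure would need a base rate that the documents do not contain. The direction of any effect on the comparison between arms is likewise unknown. The primary overall survival analysis is not affected.

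**What to change.** - **Protocol 6.3.4.** Add one sentence: the restriction does not apply to laboratory changes within an AESI category of 6.7.1; these are recorded as AEs whether or not serious, in all arms alike.
- **Before database lock.** Query sites for AESI-category laboratory deteriorations that have a dose-delay record, or a steroid, immunosuppressant or hormone-treatment record, but no matching AE. Version 12.0 is dated June 2020 and the synopsis expects the last patient to complete in Q1 2021, so a new sentence alone would reach only late events. The query brings earlier ones under the same convention. It cannot find increases that led to neither a delay nor treatment, and the study report should say so.
- **SAP 4.2.13.2.** Name amylase and lipase explicitly in the shift tables.

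This changes recording and reporting only, not patient management. The cost is one protocol sentence, a programmed check on data the study already collects, and two parameters in an existing table. The downside is more AE entries and site queries, and a slightly less favourable AE profile.
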